3.3 Patient enrollment and randomization

Investigator(s) should keep a record, the patient screening log, of patients who entered pre-study screening.

The Investigator(s) will:

1. Obtain signed informed consent from the potential patient or their guardian/legal representative before any study specific procedures are performed.
2. Assign potential patient a unique enrollment number, beginning with 'E#' through the Interactive Response Technology system. This number is the patient's unique identifier and is used to identify the patient on the electronic case report forms (eCRFs).
3. Determine patient eligibility. See Section 3.

If a patient withdraws from participation in the study, then her enrollment code cannot be reused.

This is an open-label study; there is no randomization.

3.4 Procedures for handling incorrectly enrolled patients

3.4.1 Screen failures

Screening failures are patients who do not fulfil the eligibility criteria for the study, and therefore must not be entered into the study. Patients who fail to meet the eligibility criteria should not, under any circumstances, enter the study or receive IPs. There can be no exceptions to this rule.

3.4.2 Incorrectly enrolled patients

Where a patient does not meet all the eligibility criteria but is enrolled in error, or incorrectly started on treatment, the Investigator should inform the AstraZeneca study physician immediately, and a discussion should occur between the AstraZeneca study physician and the Investigator regarding whether to continue or discontinue the patient from treatment. The AstraZeneca study physician must ensure all decisions are appropriately documented.

3.5 Methods for assigning treatment groups

Not applicable; this is a single arm study.

3.6 Methods for ensuring blinding

Not applicable; this is an open-label, unblinded, study.

3.7 Methods for unblinding

Not applicable; this is an open-label, unblinded, study.

3.8 Restrictions

Patients should not donate blood while participating in this study and for at least 3 months following the last dose of IPs.

Absorption of oral contraceptives can be impaired in case of GI symptoms such as diarrhea >24 hours or vomiting. In addition, the possibility that cediranib may induce GI CYP3A and uridine diphosphate glucuronosyltransferase (UGT) enzymes cannot be excluded and the efficacy of hormonal contraceptives may be reduced if co administered with cediranib.

Therefore, women of child-bearing potential must agree to use two highly effective forms of contraception (see Appendix J) during study treatment and for at least 6 weeks after discontinuation of study treatment and to perform pregnancy tests as required (see Sections 5.2.5.1, 6.6.1). Should a woman become pregnant or suspect she is pregnant during the study conduct, she should inform her treating physician immediately. Breast-feeding is contraindicated whilst receiving IPs.

Restrictions related to pregnancy are provided in Section 6.6. Restrictions related to concomitant medications (including medications metabolized via CYP3A4/5 or P glycoprotein (PgP)/UGT; anticoagulant therapy; anti-emetics/anti-diarrheal therapies; palliative RT and administration of other anti-cancer agents) are described in Section 7.7 and Appendix I.

Patients may not use any complementary or alternative medicines including natural herbal products or folk remedies as they may interfere with the effectiveness of the IPs.

It is prohibited to consume grapefruit juice while on olaparib therapy.

3.9 Discontinuation of investigational product

Patients may be discontinued from IPs in the following situations:

- Patient decision; the patient is at any time free to discontinue treatment, without prejudice to further treatment. A patient who discontinues treatment is normally expected to continue to participate in the study unless she specifically withdraws her consent to further participation in any study procedures and assessments (see Section 3.10.1).
- Adverse Event (AE), including AEs that meet criteria for discontinuation as defined in Section 6.7; any AEs that, in the opinion of the Investigator or AstraZeneca, contraindicates further dosing.
- Objective progression according to RECIST version 1.1 criteria.
 - Severe non-compliance with the protocol

Both IPs (cediranib and olaparib) should be discontinued at the same time; patients are not allowed to remain in the study if they are taking either cediranib or olaparib as monotherapy.

However, in rare circumstances, patients experiencing ongoing clinical benefit but who develop one of the toxicities listed below, related to one of the IPs, that prevents them to continue to take this IP, may be allowed to continue on the unrelated drug if in the opinion of the treating investigator the risk benefit remains favorable and only after discussion with the AstraZeneca Study Physician and the Principal Investigator.

AEs requiring cediranib to be discontinued:

- GI perforation
- Arterial Thromboembolic Event
- Reversible Posterior Encephalopathy Syndrome (PRES)
- Severe hemorrhage
- Severe persistent hypertension despite maximal anti-hypertensive treatment

AEs requiring olaparib to be discontinued:

- Bone marrow findings consistent with MDS/AML.
- Severe persistent anemia
- Pneumonitis

Refer to Section 6.7 for more information on the management of IP-related toxicities.

3.9.1 Procedures for discontinuation of a patient from investigational product

At any time, patients are free to discontinue IPs (ie, both cediranib and olaparib treatments) or withdraw from the study (ie, both cediranib and olaparib treatments and assessments) without prejudice to further treatment. If a patient is withdrawn from study, see Section 3.10.

A patient that decides to discontinue the IPs will always be asked about the reason(s) and the presence of any AEs. If possible, they will be seen and assessed by an Investigator(s). AEs will be followed up (see Section 6) and all study drugs should be returned by the patient.

By discontinuing from IPs, the patient is not withdrawing from the study. Any patient discontinuing the IPs should attend the scheduled Treatment Discontinuation visit, and the Follow Up visit 30 days post-discontinuation for the assessments outlined in the study schedule. After discontinuation of IPs, the Principal Investigator (PI)/Sub-Investigator will perform the best possible observation(s), test(s) and evaluation(s) as well as give appropriate

medication and all possible measures for the safety of the patient. In addition, they will record on the eCRF the date and reasons of discontinuation, any clinical manifestations and treatments required at the time of discontinuation.

Any patient who has not yet shown objective radiological disease progression at discontinuation from cediranib and olaparib treatments should continue to be followed as per RECIST as detailed in Section 4 (ie, patients should be followed for progression by tumor assessments every 8 weeks). Following objective radiological progression, patients should also be followed for survival as detailed in Section 5.1.4.

After discontinuation of the IPs at any point in the study, all ongoing AEs or serious adverse events (SAEs) must be followed until resolution unless, in the Investigator's opinion the condition is unlikely to resolve due to the patients underlying disease, or the patient is lost to follow up (see Section 6.3.2) or until the patient starts new anti-cancer treatment. All new AEs and SAEs occurring during the 30 calendar days after the last dose of IPs must be reported (if SAEs, they must be reported to AstraZeneca within 24 hours as described in Section 6.4) and followed to resolution as above. For guidance on reporting AEs after the 30 day follow up period see Section 6.3.3.

All patients must be followed for survival, up to the data cut-off for the primary analysis. If a patient is withdrawn from study, see Section 3.10.

3.10 Criteria for withdrawal

Reasons for withdrawal from the study:

- Voluntary withdrawal* by the patient who is at any time free to discontinue their participation in the study, without prejudice to further treatment.
- Incorrectly enrolled patients ie, the patient does not meet the required inclusion/exclusion criteria for the study (please refer to Section 3.4).
- Patient lost to follow-up.
- Death.

*If a patient withdraws consent, they will be specifically asked if they are withdrawing consent to continue further treatment with study medication:

- BUT are willing to remain in the study and have further follow up (eg, CT/MRI assessments, survival calls)
- OR are also withdrawing consent to follow up; thereby withdrawing consent to participate in the study

- AND if they are withdrawing consent for the use of any samples (tumor or blood) Data obtained prior to withdrawal of consent will be maintained in the clinical database and used in the study reporting (see Section 5.7.6).

3.10.1 Withdrawal of the informed consent

Patients are free to withdraw from the study at any time (IPs and assessments), without prejudice to further treatment.

A patient who withdraws consent will always be asked about the reason(s) and the presence of any AEs. The Investigator will follow up AEs outside of the clinical study.

If a patient withdraws from participation in the study, then her enrollment code cannot be reused. Withdrawn patients will not be replaced.

If the patient is lost to follow-up, the Investigator should make every reasonable effort to contact the patient or a responsible relative. Patients will be considered lost to follow-up only if no contact has been established at any time up to data cut-off for the primary analysis, such that there is insufficient information to determine the patient's status at that time. Patients who refuse to continue participation in the study, including telephone contact, should be documented as "withdrawal of consent" rather than "lost to follow-up." Investigators should document attempts to re-establish contact with missing patients throughout the study period. If contact with a missing patient is re-established, the patient should not be considered lost to follow-up and any evaluations should resume according to the protocol.

3.10.2 Survival status for withdrawn consent and lost to follow up patients

At the time of primary analysis, the survival status of all patients in the full analysis set should be re-checked, this includes those patients who withdrew consent or are classified as "lost to follow up."

- Lost to Follow up – site personnel should check hospital records, the patients' current physician, and a publicly available death registry (if available) to obtain a current survival status in the 2 weeks following data cut-off. (The SURVIVE module will be updated.)
- In the event that the patient has actively withdrawn consent to the processing of their personal data, the survival status of the patient can be obtained by site personnel from publicly available death registries or resources (if available) where it is possible to do so under applicable local laws to obtain a current survival status in the 2 weeks following data cut-off. (The SURVIVE module will be updated.)

3.11 Discontinuation of the study

The study may be stopped if, in the judgement of AstraZeneca, trial patients are placed at undue risk because of clinically significant findings that are not considered to be consistent with continuation of the study, or if the futility boundary is met at the Interim Analysis.

Regardless of the reason for termination, all data available for the patient at the time of discontinuation of follow-up must be recorded in the eCRF. All reasons for discontinuation of treatment must be documented.

In terminating the study, the Sponsor will ensure that adequate consideration is given to the protection of the patients' interests.

4. STUDY PLAN AND TIMING OF PROCEDURES

Table 5 shows the Schedule of Study Assessments.

Table 5 Schedule of study assessments

Week	Visit (window)	Screening	Treatment Period				Study treatments discontinued	Follow-up period			FPV ^m	For details, see protocol section	
			Day 1 to Week 4	Week 4 to Week 8	Week 8 onwards	Day 1 to Week 4		Week 4 to Week 8	Week 8 onwards	N/A			N/A
		Day -28 to -1	Study Day 1	Weekly (±3 days)	Every 2 weeks (±3 days)	Every 4 weeks (±3 days)	Every 8 weeks (±1 week)						
	Informed consent	X											3.3
	Determine Eligibility ^e	X											3.1/3.2
	Demographics, height	X											4.1/5.2.2
	Medical history ^d	X											4.1
	Germline BRCA status ^e	X											5.7.1
	Archival tumor tissue sample	X											5.7.2
	Adverse Events ^f	X									X		6
	Concomitant medication ^g	X									X		7.7
	Physical Examination	X	X ^h			X			X	X	X		4.1/5.2.2
	Performance Status (ECOG)	X									X		4.1
	Vital signs ⁱ , weight ^j	X	X	X	X	X			X	X	X		5.2.2/5.2.4
	ECG ^k	X									X		5.2.3

Table 5 Schedule of study assessments

Week	Visit (window)	Screenings	Treatment Period				Study treatments discontinued	Follow-up period			FPV ^m	For details, see protocol section	
			Day 1 to Week 4	Week 4 to Week 8	Week 8 onwards	Day 30 Follow-up (±3 days)		N/A	N/A	N/A			
		Day -28 to -1	Study Day 1	Weekly (±3 days)	Every 2 weeks (±3 days)	Every 4 weeks (±1 week)	Every 8 weeks (±1 week)						
	Pregnancy Test ^l For women of childbearing Potential	X ^l	X	X	X						X	5.2.5.1	
	LVEF ^m	X										6.8.3.6	
	Urinalysis ⁿ	X	X		X			X	X			5.2.1.4	
	Hematology ^{o,p}	X	X	X	X			X	X		X	5.2.1.1	
	Biochemistry ^{o,q}	X	X	X	X			X	X		X	5.2.1.2	
	CA-125	X	Every 8 weeks relative to first dose until disease progression										5.2.1.3
	TSH, FT4	X							X		X	5.2.1.2	
	Tumor assessments by CT/MRI scan ^r	X	Every 8 weeks relative to first dose until disease progression										5.1.1
	Biomarker plasma and blood PBMC samples ^s	X	Week 4	Week 8				X ^r				5.7.2	
	Blood biomarker sample for ctDNA	X						X				5.7.2	

Table 5 Schedule of study assessments

Week	Visit (window)	Screening	Treatment Period				Study treatments discontinued	Follow-up period			FPV ^a	For details, see protocol section
			Day 1 to Week 4	Week 4 to Week 8	Week 8 onwards	Day 1 to Week 4		Week 4 to Week 8	Week 8 onwards	N/A		
		Day -28 to -1	Study Day 1	Weekly (±3 days)	Every 2 weeks (±3 days)	Every 4 weeks (±1 week)	Every 8 weeks (±1 week)	Day 30 Follow-up (±3 days)	Follow-up for progression ^b	Survival Follow-up		
	EORTC-QLQ-C30/ EORTC-QLQ-OV28 (by electronic device)		X	Every 8 weeks relative to first dose until discontinuation of IPs				X				5.3.1.1
	PRO-CTCAE (by electronic device)		X	Weekly for the first 12 weeks, then every 4 weeks (relative to first dose) until discontinuation of IPs				X				5.3.1.2
	PK Sample (plasma) ^f			Week 4 only	Week 8 only							5.4.1
	Survival and subsequent anticancer therapies ^u											5.1.4
	Compliance with investigational products ^v		X	X	X	X	X	X				7.5

a. The FPV applies to patients continuing to receive clinical benefit without meeting any discontinuation criteria during the study and will occur at their last scheduled visit prior to data cut-off. Beyond FPV, patients may continue to receive cediranib and/or olaparib if they are deriving clinical benefit in the opinion of the investigator, and not fulfilling any discontinuation criteria. Such patients are to be followed in accordance with the Medical Standard of Care and as deemed appropriate by the investigators. SAE reporting (on paper) will continue to ensure safety data collection and monitoring of the patients while receiving the investigational product. Patients will continue to be monitored for all SAEs and pregnancies while receiving IPs and for 30 days after the last dose of IPs.

b. Progression follow-up only required for patients who discontinue IPs prior to disease progression

c. Review inclusion and exclusion criteria and ensure eligibility prior to enrolment

d. Obtain relevant medical history, including all treatments for ovarian cancer in the past and any unresolved toxicity.

e. All patients whose *gBRCA* status is unknown or not determined by a local test conducted in an appropriately accredited laboratory, a blood sample for prospective analysis of *gBRCA* mutation status is required during screening. Patients who do not carry deleterious or suspected deleterious germline *BRCA* mutation as determined

by a local test conducted in an appropriately accredited laboratory, may be enrolled on the basis of a documented test result; however, a blood sample is required prior to first dose of study treatments, which may be used for confirmation of the result in a retrospective analysis.

- f. Patients should be closely monitored for adverse events which should be recorded, as they occur. SAEs that occurred during screening period will also be recorded. Patient diary data (via handheld electronic device) for blood pressure and diarrhea will be reviewed by the Investigator at each patient visit and any AEs and/or SAEs recorded in the AE eCRF
- g. All concomitant treatments will be recorded while the subject is taking IPs, together with the indication for which they are used
- h. Repeat assessment not required on Day 1, if already performed during previous 7 days for screening purposes
- i. Pulse rate, systolic and diastolic blood pressure, respiration rate, pulse oxygen saturation and temperature. Blood pressure should also be measured at the clinic weekly during the first 4 weeks of treatment, and every 2 weeks from Week 4 to Week 8 and every 4 weeks thereafter. Daily home blood pressure monitoring is required via patient self-monitoring. Patients are required to check their blood pressure twice daily for at least the first 8 weeks after starting study treatment, or, if antihypertensive management is required, until a stable anti-hypertensive regimen has been established, even if this requires more than 8 weeks. After 8 weeks or once a stable regimen has been achieved, blood pressure monitoring may be reduced to once daily. Daily blood pressure monitoring is required for as long as the patient remains on cediranib treatment and for 30 days after cediranib discontinuation, or until the FPV. Daily blood pressure monitoring by the patient will be recorded using a handheld electronic device See Section 5.2.4.1.
- j. Required at baseline, at every 8 weeks, until treatment discontinuation and at the 30-day safety follow-up visit, or until the FPV.
- k. ECGs are required within 7 days prior to starting IPs, and when clinically indicated thereafter. Any clinically significant changes on all other visits should be recorded as adverse events.
- l. Required for women of childbearing potential within 7 days prior to the start of IPs, every 4 weeks thereafter during study treatment. Pregnancy test for women of childbearing potential is required at the FPV and every 4 weeks thereafter until treatment discontinuation.
- m. Left Ventricular Ejection Fraction required for patients with prior treatment with anthracyclines, or prior treatment with trastuzumab or central thoracic radiation therapy (RT) including exposure of heart to therapeutic doses of ionizing RT, history of myocardial infarction within 6-12 months prior to enrolment or history of other significant impaired cardiac function. For these patients LVEF will be done at screening and thereafter as clinically indicated, and per recommendations following review of initial safety data by the sponsor (see Table 16).
- n. At screening, UPC ≤ 1 , OR proteinuria $\leq 2+$ on two consecutive dipsticks taken no less than 1 week apart, is required. Patients with 2+ proteinuria on dipstick must also have UPC < 0.5 on 2 consecutive samples. Refer to Section 5.2.1.4 for information on management of patients with potential nephrotic syndrome.
- o. Repeat assessment not required on Day 1, if already performed during previous 7 days for screening purposes.
- p. Full Blood Count as per Section 5.2.1.1: hemoglobin, platelets, mean cell volume, white blood cell count, absolute neutrophil count and absolute Lymphocyte count
- q. Biochemistry (sodium, magnesium, calcium, potassium, albumin, total protein, creatinine, total bilirubin, AL.T, AST, alkaline phosphatase). Creatinine clearance (Cockcroft-Gault or another validated method); to be calculated at baseline and re-calculated as clinically indicated during study conduct.
- r. Baseline tumor assessment should include CT/MRI of the chest, abdomen and pelvis. Follow-up CT/ MRI tumor assessments will cover chest (in those patients with disease in the chest or upper abdomen lymphadenopathy at baseline), abdomen and pelvis. Any other sites at which new disease is suspected should also be appropriately imaged. Baseline radiological imaging is required within 4 weeks prior to first dose of investigational products (IPs). Follow up assessments should be done every 8 weeks after first dose of IP until objective radiological disease progression, withdrawal of consent or the primary analysis.
- s. Blood samples for PBMC testing (8 mL) and plasma biomarker testing (6 mL) will be taken at baseline; at Week 4; at Week 8 and treatment discontinuation. Details to be found in the lab manual.
- t. Eight PK samples per patient (4 samples for cediranib and 4 samples for olaparib) will be collected at steady state: 2 samples on Week 4 and 2 samples on Week 8 visit for cediranib and olaparib each. At the Week 4 visit, the first 2 samples should be taken 0.5 hours prior to the first dose of cediranib at the Week 4 visit; the second 2 samples should be taken 1 to 3 hours after the first dose of olaparib at the Week 4 visit. At the Week 8 visit, 2 samples should be taken 0.5 hours prior to the dose of cediranib administration; the second 2 samples should be taken 1 to 3 hours after the first dose of olaparib at the Week 8 visit.
- u. Assessments for survival should be made every 8 weeks (relative to first dose) following objective disease progression. Survival information may be obtained via telephone contact with the patient, patient's family or by contact with the patient's current physician. Subsequent anticancer therapies should also be recorded. Patients should be contacted or other data sources checked (see Section 3.10.2) in the 2 weeks following the data cut-off for the primary analysis to provide current complete survival data.

- v. Missed doses of study medications will be reported by patients using a handheld electronic device. These data will be reviewed by the Investigator at each patient visit and data entered in eCRF.
- Abbreviations: AE adverse event; ALT alanine transferase; AST aspartate transferase; *BRCA* breast cancer resistance protein; CA-125 cancer antigen-125; CT computed tomography; ctDNA circulating tumor DNA; ECG electrocardiogram; ECOG Eastern Cooperative Oncology Group; eCRF electronic case report form; EORTC European Organization for Research and Treatment of Cancer; FPV final protocol visit; FT4 free thyroxine; IP investigational product; LVEF left ventricular ejection fraction; MRI magnetic resonance imaging; N/A not available; PBMC peripheral blood mononuclear cells; PK pharmacokinetics; PRO-CTCAE Patient-Reported Outcomes version of the Common Terminology Criteria for Adverse Events; QLQ quality of life questionnaire; SAE serious adverse event; TSH thyroid stimulating hormone; UPC urine protein:creatinine ratio.

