4.4 Final protocol visit

Patients who continue to receive clinical benefit without meeting any discontinuation criteria during the study, will complete a FPV which will occur at their last scheduled visit prior to data cut-off for the primary analysis. Beyond the FPV, patients may continue to receive cediranib and/or olaparib if they are deriving clinical benefit in the opinion of the investigator, and not fulfilling any discontinuation criteria.

Beyond the FPV, patients continuing to receive IPs are to be treated as described in Section 4.5.

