4.5 End of study

The end of the study is defined as 'the last visit of the last patient undergoing the study' (ie, last subject last visit [LSLV]) or when the Sponsor decides to discontinue the study.

There will be a primary data cut-off defined at approximately 8 months (LSLV) after the last patient received her first dose of study treatment. This primary data cut-off will be followed by clinical database lock when all data for all patients have been collected. The primary data analysis will be performed and a Clinical Study Report (CSR) written based on this data set.

Patients who continue to receive clinical benefit without meeting any discontinuation criteria during the study, will complete a FPV which will occur at their last scheduled visit prior to primary data cut-off. Beyond the FPV, patients may continue to receive cediranib and/or olaparib (to be provided by the Sponsor), if they are deriving clinical benefit in the opinion of the investigator, and not fulfilling any discontinuation criteria.

Such patients are to be followed in accordance with the Medical Standard of Care and as deemed appropriate by the Investigators. Serious adverse event reporting (on paper) will continue to ensure safety data collection and monitoring of the patients while receiving the investigational product. It is recommended that investigators continue to observe ongoing patients at the frequency employed prior to the FPV. Protocol dose modification and stopping criteria are to be followed while a patient is receiving cediranib and/or olaparib. Restrictions regarding concomitant medications (Section 7.7) must be followed while the patient is receiving cediranib and/or olaparib. A change in the dose/schedule of cediranib and/or olaparib should only occur for safety reasons, based on the Investigator's judgement, and should generally follow the approach for dose reduction and discontinuation as described in this protocol. Combining cediranib and/or olaparib with other anti-cancer therapy is not allowed.

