5.2.4.1 Pulse and blood pressure

Since rapid changes in BP can occur with cediranib treatment with the potential for life-threatening complications if hypertension is not appropriately managed, all patients should check their BP twice daily for at least the first 8 weeks after starting IPs, or, if antihypertensive management is required, until a stable anti-hypertensive regimen has been established, even if this requires more than 8 weeks. After 8 weeks or once a stable regimen has been achieved, BP monitoring may be reduced to once daily. Twice daily monitoring should be re-implemented after any cediranib dose interruption for at least two weeks or until the patient is re-established on a stable antihypertensive regimen, whichever takes longer.

Patients should continue to check their BP for as long as they remain on cediranib treatment and for 30 days after cediranib discontinuation. Patients will record their BP data using handheld electronic devices, to be provided by the study Sponsor.

Patient BP will be measured during routine study visits: weekly during the first 4 weeks, every 2 weeks during the next 4 weeks and every 4 weeks thereafter to ensure that BP guidelines are being correctly followed. During routine study visits, BP and pulse rate will be measured preferably using a semi-automatic BP recording device with an appropriate cuff size after 10 minutes rest. For timings of assessments refer to the Schedule of Assessments (see [Table 5](#)).

The date of collection and measurement will be recorded on the appropriate eCRF.

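### Table 5 footnote i lets required daily home blood pressure checks end at the final protocol visit, while Section 5.2.4.1, which it cites, ties them to cediranib treatment plus 30 days

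*Protocol*

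**What the plan says.** The protocol states the end of home BP monitoring in two places, with different results.

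- **Table 5, footnote i.** Daily monitoring is required during cediranib treatment "and for 30 days after cediranib discontinuation, or until the FPV". The footnote closes with a pointer: "Daily blood pressure monitoring by the patient will be recorded using a handheld electronic device See Section 5.2.4.1".
- **Section 5.2.4.1.** "Patients should continue to check their BP for as long as they remain on cediranib treatment and for 30 days after cediranib discontinuation". There is no FPV end point. The section gives its reason: BP can change quickly on cediranib, "with the potential for life-threatening complications if hypertension is not appropriately managed".

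The FPV is not the end of treatment. Section 4.4 says: "Beyond the FPV, patients may continue to receive cediranib and/or olaparib if they are deriving clinical benefit". Footnote a describes care from then on: "Such patients are to be followed in accordance with the Medical Standard of Care and as deemed appropriate by the investigators". Section 4.5 adds: "It is recommended that investigators continue to observe ongoing patients at the frequency employed prior to the FPV", and Section 9.3 repeats this. Both sections keep the protocol's dose-modification and stopping rules in force while either drug is taken. Neither mentions home BP.

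Section 6.8.3.1 describes the home checks again as part of hypertension management and sets no FPV limit.

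**The concern.** For a patient who passes the FPV and stays on cediranib, the assessment schedule says the requirement has ended, and the detailed section says it has not. No text says which governs. Sites tend to work from the schedule table, so a site could reasonably stop home checks at the FPV.

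What is at stake is patient safety. The Table 12 dose rules still bind these patients. They sort events by whether a rise lasts less or more than 24 hours, and for patients on multi-drug antihypertensive therapy they turn on whether BP is below 150/100 mmHg at 48 hours. Occasional clinic readings alone do not supply that information. Section 6.8.3.1 also returns patients to twice-daily checks after any cediranib interruption, so the protocol does not treat the risk as confined to the first weeks. It warns too that BP is expected to fall when cediranib is stopped or reduced. Under footnote i, the 30 days of checks after stopping would also be lost for anyone who stops after the FPV.

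Section 1.1.4.3 shows that the hazard is real. In the Phase II combination study, grade 3 or 4 hypertension was 41% with the combination and 0% with olaparib alone. The one grade 4 hypertension event was in a patient who had not fully complied with BP monitoring. One case proves no cause.

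**Working it through.** **Comparison of the texts.** The plan gives no figure to reproduce on this point, so the check is a reading of the two rules for each kind of patient.

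| Patient | End under footnote i | End under Section 5.2.4.1 |
|---|---|---|
| Stops cediranib before any FPV | Discontinuation + 30 days | Discontinuation + 30 days |
| Passes the FPV and stays on cediranib | FPV | Last cediranib + 30 days |

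The rules differ only in the second row, which is the group for whom the FPV exists.

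**Is the difference deliberate?** Two features suggest that it was not fully worked through.

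- When the protocol wants a named check to continue after the FPV, it says so. Footnote l and Section 5.2.5.1 require pregnancy tests at the FPV and every 4 weeks afterwards until treatment stops.
- Sections 5.2.1.2, 5.2.2 and 5.2.5.1 all mention the FPV, and Section 5.2.4.1 does not. This fits version 5.0 having added the FPV without carrying it through every section.

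**How many patients?** Inputs from Section 8.2: about 60 patients, 80% PFS events at cut-off, median PFS 6 months.

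- Expected event-free at cut-off: 60 × (1 − 0.80) = 12.
- Expected event-free 4 weeks earlier, if the FPV falls then and the hazard is exponential: 12 × exp[(ln 2 / 6) × (28 / 30.44)] = 12 × 1.11 ≈ 13.
- Sensitivity: the 73% that Section 8.2 gives for the original recruitment plan would leave 60 × (1 − 0.73) ≈ 16. That percentage belongs to a different schedule and is used only to show that the count moves with the assumption.

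Event-free is a proxy for being on cediranib. It includes patients who stopped cediranib for toxicity or who continue on olaparib alone.

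**How late in treatment?** Cut-off is 8 months after the last patient's first dose. With 4-weekly visits, her FPV is at about 8 − 28/30.44 = 7.1 months or later. Patients who started earlier are further on.

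**What gap could arise?** If a site stopped home checks but kept 4-weekly visits, routine readings would go from 1 day apart to 28 days apart, or 28 + 3 + 3 = 34 days at the edges of the ±3-day window. This is conditional. It requires the site to follow footnote i over Sections 5.2.4.1 and 6.8.3.1, and the visits themselves are only recommended after the FPV.

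**The case against.** The strongest reply is that the two texts can be reconciled. Table 5 schedules study assessments, the sentence after the FPV clause concerns the handheld device, and footnote j uses much the same ending for weight: "until treatment discontinuation and at the 30-day safety follow-up visit, or until the FPV". On that reading footnote i only closes data capture, and Section 5.2.4.1 remains the clinical instruction. Table 5 also sends the reader to Section 5.2.4 twice, in footnote i and in the vital-signs row. Following Table 12 in practice implies readings between visits, and Table 12 increases monitoring once hypertension is found.

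Much of this is fair. Data capture may have been the intent. But the FPV clause sits in the sentence that makes monitoring a requirement, and device recording is a separate sentence. Table 12's added checks begin only once a raised reading has been found, and routine home checks are what would find it between visits. Standard-of-care follow-up and a recommended visit frequency do not name home BP.

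It is also fair that the protocol stresses early risk, with rises within hours of starting, and that these patients are months past that point. This lowers the urgency without resolving the conflict.

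Four stronger readings are tempting and are not supported.

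- **Footnote i forbids home checks after the FPV.** It does not. It only ends the requirement.
- **At most 12 patients are affected.** Twelve is an expectation under an assumed median PFS, and longer PFS would give more.
- **The plan produces gaps of 28 to 34 days.** It does so only if a site sets two other sections aside.
- **Study results are affected.** Section 8.4.3 keeps electronically collected BP data out of the clinical study report, and no endpoint uses them.

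**Conclusion.** The conflict is in current text and should be corrected. For patients who stay on cediranib after the FPV, the schedule ends a safety check that Section 5.2.4.1 ties to exposure, while the dose rules that depend on BP continue. It goes beyond a clerical slip, because following the schedule as written drops the check.

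The scale is small: about 12 of 60 patients expected to be event-free at cut-off (about 13 four weeks earlier), each about 7 months or more from first dose. These figures rest on the plan's 80% PFS-event assumption and, for the second, on an exponential hazard. The documents give no estimate of how many will still be taking cediranib, and nothing in them shows that sites would in fact stop the checks. The consequence is limited to safety conduct after the FPV. The primary analysis, the sample size and the reported safety outputs are untouched.

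**What to change.** - **Footnote i:** delete the FPV clause from the home BP sentence, or replace it with wording such as: including after the FPV while the patient remains on cediranib.
- **Sections 4.5 and 9.3:** add one sentence saying that home BP checks under Sections 5.2.4.1 and 6.8.3.1 continue after the FPV while the patient is on cediranib and for 30 days after it stops.
- **Section 5.2.4.1:** leave as it is. A cut-off for handheld-device recording would be new policy and is not needed to resolve the conflict.
- **Meanwhile:** a letter to investigators, which Section 1.5 names as a way to address safety issues, can alert sites until the amendment is approved.

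The cost is a small self-check burden for the few patients still on cediranib, plus routine ethics committee or IRB approval under Section 10.5 across approximately 40 sites.
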